12.1.2 Disease Parameters

Measurable disease. Measurable lesions are defined as those that can be accurately measured in at least one dimension (longest diameter to be recorded for non-nodal lesions and short axis for nodal lesions) as >20 mm by chest x-ray, as >10 mm with CT scan or MRI, or >10 mm with calipers by clinical exam. All tumor measurements must be recorded in millimeters (or decimal fractions of centimeters).

Non-measurable disease. All other lesions (or sites of disease), including small lesions (longest diameter <10 mm or pathological lymph nodes with ≥ 10 to <15 mm short axis), are considered non-measurable disease. Bone lesions, leptomeningeal disease, ascites, pleural/pericardial effusions,

MEMORIAL SLOAN-KETTERING CANCER CENTER
IRB PROTOCOL

IRB#: 14-140 A (7)

lymphangitis cutis/pulmonitis, inflammatory breast disease, and abdominal masses (not followed by CT or MRI), are considered as non-measurable.

Target lesions. All measurable lesions up to a maximum of 2 lesions per organ and 5 lesions in total, representative of all involved organs, should be identified as target lesions and recorded and measured at baseline. Target lesions should be selected on the basis of their size (lesions with the longest diameter), be representative of all involved organs, but in addition should be those that lend themselves to reproducible repeated measurements. It may be the case that, on occasion, the largest lesion does not lend itself to reproducible measurement in which circumstance the next largest lesion which can be measured reproducibly should be selected. A sum of the diameters (longest for non-nodal lesions, short axis for nodal lesions) for all target lesions will be calculated and reported as the baseline sum diameters. If lymph nodes are to be included in the sum, then only the short axis is added into the sum. The baseline sum diameters will be used as reference to further characterize any objective tumor regression in the measurable dimension of the disease.

Non-target lesions. All other lesions (or sites of disease) including any measurable lesions over and above the 5 target lesions should be identified as non-target lesions and should also be recorded at baseline. Measurements of these lesions are not required, but the presence, absence, or in rare cases unequivocal progression of each should be noted throughout follow-up.

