The secondary endpoints of the phase 1b portion are (1) Response Rate (RR) defined by RECIST 1.1 criteria and by CHOI criteria, (2) Progression Free Survival (PFS), (3) Clinical Benefit Rate (CBR) at 32 weeks, and (4) BGJ398 pharmacokinetic parameters, such as area under the curve (AUC) and maximum concentration (C_{max}). RR will be estimated as the proportion of patients who have complete response or partial response for each criterion. PFS will be calculated using Kaplan-Meier estimate among all patients enrolled at each dose level. Patients who have not experienced the event of interest by the end of the study will be censored at the time of the last follow-up. Plasma concentrations of BGJ398 will be analyzed at multiple time points and expressed as a mean +/- SE.

The phase 1b portion of the study will have a minimum sample size of 6 patients and a maximum of 30. We expect to accrue approximately 2 patients each month, and hence expect to finish the phase 1b portion of the study in approximately 9-15 months.

Evaluable patients for safety analysis include all patients who have received one dose of imatinib plus BGJ398. Patients who stop therapy before Cycle 2, Day 1 for reasons other than toxicity will be replaced in the Phase I study for the purposes of evaluating the DLT. Evaluable patients for efficacy include all patients who have received one dose of imatinib plus BGJ398. Patients who are missing an assessment of response post baseline will be considered non-responders for that time point.

Patients on the Phase I portion of the study will not be included in the final efficacy analysis due to differences in the eligibility criteria in the two phases.

Phase 2 Portion Study Design and Endpoint Assessment

The primary endpoint of the phase II portion of the study is to assess Response Rate (CR+PR, RECIST 1.1) after 32 weeks of combination therapy. In order to detect a 20% improvement in the RR over imatinib alone (unacceptable rate of 45%; acceptable rate of 65%), 44 Phase II patients will be enrolled. At the end of the study, if > 24 patients have had a documented response by RECIST 1.1, the study will be considered positive and the treatment regimen will be considered worthy of further investigation. The study design is based on an exact Binomial test and has a one-sided type I error of 0.08 and a type II error of 0.1.

We expect to accrue 2 patients each month, and hence expect to finish the phase 2 portion of the study in 24 months.

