For the purpose of exploratory studies, the phase 2 portion includes the phenotypic (by IHC), genetic, transcriptomic, epigenetic, and pharmacodynamic characterization of the tumors as correlative endpoints. Twenty patients are planned to have mandatory paired biopsies (pre and post treatment), and the remaining patients will provide optional biopsies if funding is identified. This sample size provides 80% power to detect a standardized difference of 0.55 assuming 2 sided one sample paired t test at 10% significance level. The variable of interest will be change in protein levels.

The analysis of the exploratory studies is planned as follows.

- 1) ETV1 protein level by western blot (WB) as a continuous variable. The change of ETV1 protein level (before vs. after the combination therapy) will be recorded as up, down, and no-change (categorical response). It will be tabulated with the percentages provided. It will be correlated with response using the Fisher's exact test.
- 2) ETV1-dependent transcriptome (expression profile of ETV1-dependent gene targets) by nanostring. The expression change of ETV1 target genes (before vs. after the combination therapy) will be correlated with clinical response using the Wilcoxon rank test. The outcome will be a composite score (based on gene expression level and directionality of the changes), and it is continuous variable.
- 3) Cell proliferation (Ki-67) and apoptosis (cleaved caspase-3) by IHC. Descriptive statistics will be provided. These variables are continuous.
- 4) MAP kinase pathway and other pathways downstream of KIT and FGF signaling using standard antibodies (phospho-ERK, phospho-KIT, phospho-MEK, phospho-AKT, etc) by IHC. Descriptive statistics will be provided.
- 5) KIT/PDGFRα mutational status in matched tumor biopsy specimens collected prior to therapy, after combination therapy and upon disease progression. FGFR and FGF2 expression on tumor

MEMORIAL SLOAN-KETTERING CANCER CENTER IRB PROTOCOL

IRB#: 14-140 A (7)

samples by IHC analyzed as a binary covariate and FGF2 ligand levels in collected serum by ELISA analyzed as a continuous covariate.

- 6) Protein expression of FGF2, sVEGFR1, sVEGFR2, VEGF-A, -C, -D, cKIT, PLGF, and Tie2 in tumor tissues utilizing commercially available immunoassay kits. This will be a continuous variable.

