- 7) Expression of genes implicated in GIST pathogenesis and signaling, including KIT, ETV1, FGFR1, -2, -3, and -4; DUSP6, SPRY2, and SPRY4 will be analyzed as a continuous covariate. Changes before and after treatment will be assessed and correlated with clinical response.

In most of the above studies, we are interested in looking at changes in expression levels, protein measurements, or mutation status before and after treatment. The correlative endpoints described above will be correlated with response (binary outcome defined as CR+PR using RECIST 1.1). These analyses are exploratory in nature and no adjustment for multiple comparisons will be made.

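### Section 14 relates the tumour correlatives only to binary CR+PR; adding percent change in target-lesion size, already recorded, would gain power with 20 biopsy pairs

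*Combined protocol and SAP*

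**What the plan says.** Section 14.0 lists seven groups of exploratory analyses and closes with a general rule: "The correlative endpoints described above will be correlated with response (binary outcome defined as CR+PR using RECIST 1.1". Within the list, the continuous composite score for ETV1-dependent genes (item 2) "will be correlated with clinical response using the Wilcoxon rank test". Item 7 relates changes in gene expression to clinical response. For ETV1 protein (item 1), change is recorded as up, down or unchanged, and "It will be correlated with response using the Fisher's exact test". Item 3 reads "Cell proliferation (Ki-67) and apoptosis (cleaved caspase-3) by IHC. Descriptive statistics will be provided", and item 4 is likewise descriptive, although the closing rule covers both.

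On numbers, "Twenty patients are planned to have mandatory paired biopsies (pre and post treatment", and "This sample size provides 80% power to detect a standardized difference of 0.55 assuming 2 sided one sample paired t test at 10% significance level". That statement concerns within-patient change in protein level.

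On tumour size, Section 12.1.2 says: "The baseline sum diameters will be used as reference to further characterize any objective tumor regression in the measurable dimension of the disease". Section 12.1.10 has actual measurements recorded at each later evaluation, with default values for lesions too small to measure. Scans are 8-weekly to week 32. Under Section 12.1.4.1, target-lesion PR is a decrease of at least 30% in this sum.

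For blood, Section 10.2 (the FGF2 ELISA paragraph and items 4 and 5) relates FGF2 and imatinib levels to the primary and secondary outcomes.

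**The concern.** Cutting size change at 30% treats a 31% and an 80% shrinkage as the same result, and 29% and 31% as opposite results. The primary test needs the cut because it compares a response rate with a historical one. The correlatives have no historical comparator, and the plan gives no reason for using the cut there.

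The correlatives are meant to help select patients for FGFR inhibition (Section 3.1.6) and to shape later trials (Section 1.0), and 20 patients have mandatory paired biopsies for them. At a 65% response rate, 20 × 0.65 = 13 responders are compared with 7 non-responders. The plan does not consider power for association with response.

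**Working it through.** **The plan's own figure.** Inputs from Section 14.0: n = 20, standardized difference 0.55, two-sided 10%.

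- Normal approximation: Φ(0.55 × √20 − 1.645) = Φ(2.460 − 1.645) = Φ(0.815) = 79.2%, which reproduces the stated 80%.
- Exact noncentral t with 19 degrees of freedom: 76.6%.

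Response does not enter this calculation, so the choice of outcome cannot change it.

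**Power for association with response.** Inputs from the documents: 20 pairs, and response rates of 45% and 65% ("unacceptable rate of 45%; acceptable rate of 65" per cent). The correlation between marker change and tumour-size change is an assumption, varied from 0.3 to 0.7.

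Method: draw marker change and size change as bivariate normal with correlation ρ, and call the best 65% (or 45%) of the size distribution responders. Compare the exact Wilcoxon test on responders versus non-responders with Spearman's test on the uncut size change, using 20,000 simulated trials per setting. At 65%:

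| ρ | 5%: Spearman | 5%: Wilcoxon | Gain (points) | 10%: Spearman | 10%: Wilcoxon | Gain (points) |
|---|---|---|---|---|---|---|
| 0.3 | 23.1% | 15.1% | 8.0 | 34.0% | 25.1% | 8.9 |
| 0.4 | 38.2% | 24.6% | 13.6 | 51.4% | 37.5% | 13.9 |
| 0.5 | 57.0% | 36.7% | 20.3 | 69.7% | 51.4% | 18.3 |
| 0.6 | 77.1% | 54.0% | 23.1 | 85.9% | 67.9% | 18.0 |
| 0.7 | 92.0% | 72.1% | 19.9 | 95.7% | 83.3% | 12.4 |

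Repeat runs with fewer replicates move single differences by a point or two. I therefore quote 13 to 24 points at 5% and 14 to 20 at 10% for ρ of 0.4 to 0.6, and 8 to 10 at ρ = 0.3. At a 45% response rate the gains for ρ of 0.4, 0.5 and 0.6 are 12.3, 18.0 and 20.2 points at 5%, and 12.8, 16.6 and 15.4 at 10%. Null rejection stays close to or slightly below nominal for both tests.

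**Effect of a worst-rank rule.** Percent change needs a rule for progression through new or non-target lesions and for patients with no post-baseline scan. Two extremes bracket the effect at 65% and the 5% level:

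- If the 15% given the worst rank are also the worst on tumour size, Spearman loses no more than about 1 point.
- If they are unrelated to marker and size, then at ρ = 0.5 with 15% affected (20 × 0.15 = 3 patients) Spearman falls from 56% to about 32% and Wilcoxon from 37% to about 25%, a gain of about 7 points.

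In the second case, over ρ of 0.4 to 0.6, the gain is 5 to 9 points with 15% affected, 7 to 15 with 10%, and 10 to 18 with 5%.

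**What the figures cover.** They apply to continuous markers on the 20 biopsy pairs. They do not model ETV1 protein recoded for Fisher's test, which is a separate loss. Nor do they apply to blood markers, which are drawn from all 44 planned Phase II patients.

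**The case against.** The strongest case against is that these analyses are declared exploratory, and that tying them to the primary endpoint is coherent and easy to interpret. RECIST response also carries information that target-lesion size does not: new and non-target lesions count, responses must be confirmed (Section 12.1.9), and they are subject to central review (Section 16.1.2). Best percent change is unconfirmed and can be distorted by the surgery or embolization that Section 13.0 permits. Mutation status and binary IHC covariates (item 5) have no continuous scale. All of this stands. It is why percent change should be added beside CR+PR rather than put in its place, and only for continuous markers.

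A reader might infer three stronger points that the documents do not support.

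- *That every tumour and blood correlative is confined to CR+PR.* Section 10.2 relates FGF2 and imatinib levels to the primary and secondary outcomes, and in Section 14 the latter include PFS and OS. What is true of the blood markers is that continuous tumour change is not named for them either, and that Section 14 does not carry the Section 10.2 analyses forward.
- *That the planned test would usually miss a real relation.* At 5% this holds for correlations up to 0.5, but power is 54% at 0.6. At 10%, the level used in the plan's own power statement, it is 51% at 0.5 and 68% at 0.6.
- *That the stated 80% power is undermined.* It concerns within-patient change and does not involve response.

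**Conclusion.** The point holds for the tumour correlatives in Section 14: a more informative outcome is already in the data and no analysis uses it. Every setting tried favours the uncut outcome, but the size of the gain is conditional. The 13 to 24 points require a true correlation of 0.4 to 0.6, roughly bivariate normal data, and few patients placed at the worst rank for unrelated reasons. Under less favourable assumptions the gain is 5 to 10 points. This is a worthwhile low-cost improvement to exploratory work. The primary endpoint and its decision rule are not in question.

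**What to change.** Add to the closing paragraph of Section 14:

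*For correlatives measured on a continuous scale, association with the best percent change in the sum of target-lesion diameters within 32 weeks, using scans before any resection or local procedure on target lesions, will also be assessed by Spearman rank correlation. Patients with PD due to new or non-target lesions, or with no post-baseline scan, take the worst rank; a sensitivity analysis excludes them. Association with CR+PR will be reported alongside. Categorical correlatives (mutation status, binary IHC) keep the CR+PR analysis.*

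In the same edit, refer to the blood-marker analyses of Section 10.2 so that the two sections agree.

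The cost is one more analysis per continuous marker, plus the sensitivity analysis, and an outcome that is unconfirmed and not identical to the primary endpoint. No new visits, scans or samples are needed.

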15.0 RESEARCH PARTICIPANT REGISTRATION AND RANDOMIZATION PROCEDURES

15.1 Research Participant Registration

Confirm eligibility as defined in the section entitled Criteria for Patient/Subject Eligibility.

Obtain informed consent, by following procedures defined in section entitled Informed Consent Procedures.

During the registration process registering individuals will be required to complete a protocol specific Eligibility Checklist.

All participants must be registered through the Protocol Participant Registration (PPR) Office at Memorial Sloan-Kettering Cancer Center. PPR is available Monday through Friday from 8:30am – 5:30pm at [contact]. Registrations must be submitted via the PPR Electronic Registration System (<http://ppr/>). The completed signature page of the written consent/RA or verbal script/RA, a completed Eligibility Checklist and other relevant documents must be uploaded via the PPR Electronic Registration System.

15.1.1 Registration for Participating Sites

Central registration for this study will take place at Memorial Sloan-Kettering Cancer Center (MSKCC).

To complete registration and enroll a participant from another institution, the study staff at that site must contact the designated research staff at MSKCC to notify him/her of the participant registration. The site staff then needs to email registration/eligibility documents to the Multicenter Trial Core at MSKCC at [contact].

The following documents must be sent for each enrollment within 24 hours of the informed consent form being signed:

- The completed or partially completed MSKCC eligibility checklist

MEMORIAL SLOAN-KETTERING CANCER CENTER IRB PROTOCOL

IRB#: 14-140 A (7)

- The signed informed consent and HIPAA Authorization form
- Supporting source documentation for eligibility questions (laboratory results, pathology report, radiology reports, MD notes, physical exam sheets, medical history, prior treatment records, and EKG report)

Upon receipt, the research staff at MSK will conduct an interim review of all documents. If the eligibility checklist is not complete or source documentation is missing, the participant will be registered PENDING and the site will be responsible for sending the completed registration documents within 30 days of the consent.

If the external registration submission is complete, the participating site IRB has granted approval for the protocol, and the site is in good standing, the MSK research staff will send the completed registration documents to the MSK PPR Office for participant enrollment as stated in section [15.1](#).

Once the participant is registered, the participant will be assigned a number in the MSK Clinical Research Database (CRDB). This number is unique to the participant and must be written on all data and correspondence for the participant. This protocol participant number will be relayed back to study staff at the registering site via e-mail and will serve as the enrollment confirmation.

15.2 Randomization

NOT APPLICABLE

16.0 DATA MANAGEMENT ISSUES

A Research Study Assistant (RSA) will be assigned to the study. The responsibilities of the RSA include project compliance, data collection, abstraction and entry, data reporting, regulatory monitoring, problem resolution and prioritization, and coordinate the activities of the protocol study team.

The data collected for this study will be entered into a secure database (MediData RAVE). Source documentation will be available to support the computerized patient record.

16.0.1 *Data and Source Documentation for Participating Sites*

Data

The participating site(s) will enter data remotely into an internet-based Electronic Data Capture system, termed MediData RAVE. Standardized Electronic Case Report Forms (eCRFs) and data entry guidelines have been generated for this study. The site staff will receive MediData RAVE training prior to enrolling its first patient through a series of e-Modules. The participating Site PI is responsible for ensuring these forms are completed accurately and in a timely manner. Participating sites will be responsible for filling out these eCRFs and submitting them to MSKCC per the designated timelines.

Source Documentation

Source documentation refers to original records of observations, clinical findings and evaluations that are subsequently recorded as data. Source documentation should be consistent with data entered into eCRFs. Relevant source documentation to be reviewed by the study monitor throughout the study includes:

MEMORIAL SLOAN-KETTERING CANCER CENTER
IRB PROTOCOL

IRB#: 14-140 A (7)

- Baseline measures to assess pre-protocol disease status (ex. CT,PET Scan, EKG, ECHO, MUGA, etc.)
- Treatment records
- Grade 3-5 toxicities/adverse events not previously submitted with SAE Reports
- Response designation

Source documentation should include a minimum of two identifiers to allow for data verification. MSK will maintain the confidentiality of any subject-identifiable information it may encounter.

16.0.2 Data and Source Documentation Submission for Participating Sites

Participating sites should enter data directly into MediData RAVE. Source documentation should be sent to MSKCC at the contact provided below. Submissions should include a cover page listing relevant records enclosed per participant.

Contact for submission of Source Documentation

EMAIL: [contact] to the attention of the Multicenter Trial Core Research Staff

16.0.3 Data and Source Documentation Submission Timelines for Participating Sites

Data and source documentation to support data should be transmitted to MSKCC according to the following chart:

Data and Source Submission Requirements and Timelines for Therapeutic Studies

	Baseline	Every Cycle	SAE	Off Study
SUBMISSION SCHEDULE				
Source Documentation	Within 24 hours (see section 15.1.1)	Within 14 days of visit	Within 48 hours of event (see section 17.3); updates to be submitted as available	Within 14 days of visit
eCRFs	Within 7 days of visit			
Required Forms				
Baseline Forms	X			
Cycle Forms		X		
Off Study Forms				X
Concomitant Medications Form	X	X	X	X
Adverse Event Form		X	X	
Serious Adverse Event Form			X	

MEMORIAL SLOAN-KETTERING CANCER CENTER
IRB PROTOCOL

IRB#: 14-140 A (7)

16.0.3 Data Review and Queries for Participating Site Data

Research staff at MSKCC will review data and source documentation as it is submitted. Data will be monitored against source documentation and discrepancies will be sent as queries to the participating sites. Queries will be sent by MSK Research staff twice a month.

Participating sites should respond to data queries within 14 days of receipt.

16.1 Quality Assurance

Weekly registration reports will be generated to monitor patient accruals and completeness of registration data. Routine data quality reports will be generated to assess missing data and inconsistencies. Accrual rates and extent and accuracy of evaluations and follow-up will be monitored periodically throughout the study period and potential problems will be brought to the attention of the study team for discussion and action

Random-sample data quality and protocol compliance audits will be conducted by the study team, at a minimum of two times per year, more frequently if indicated.

16.1.1 Quality Assurance for Participating Sites

Monitoring

Each data collection site will be monitored periodically by MSKCC or a designated contract research organization (CRO). Monitoring visits will be conducted every 4-8 weeks, dependent upon the protocol and patient accrual and activity. The monitor and the participating site will identify a mutually agreeable time for each monitoring visit. At least 10 business days ahead of the visit, the monitor will send the site a notification letter that details the date and expectations of the visit. Monitoring may be conducted remotely or in-person. The monitor must be allowed access to all protocol regulatory and source documents to assess compliance with the protocol, federal regulations and GCPs. The monitor will assess all data for completeness of source documents and to confirm data being recorded in the eCRFs is accurate. If monitoring will be done remotely, sites must agree in advance to provide source documents as required. During onsite visits, the monitor will also inspect and review the facilities and investigational product storage area. The participating site will maintain accurate records of dispensing of study drugs for drug accountability. Drug accountability will be reviewed at monitoring visits. Study drug and bottles must be retained until the monitor performs drug accountability of the study drug(s).

The site Investigator(s) and/or an authorized member of the Investigator's staff should allow sufficient time during monitoring visits to discuss findings. The Investigator(s) or an authorized member of the Investigator's staff will make any necessary corrections during and between monitoring visits.

Auditing

MEMORIAL SLOAN-KETTERING CANCER CENTER IRB PROTOCOL

IRB#: 14-140 A (7)

Each participating site accruing participants to this protocol will be audited by MSK for protocol and regulatory compliance, data verification and source documentation. Audits of selected participant records may be conducted on-site or remotely.

Audits will be conducted annually at minimum, and more often if significant and/or repeated findings are identified during monitoring visits. The number of participants audited will be determined by the outcome of monitoring visits and complexity of the protocol.

Each audit will be summarized and a final report will be sent to the PI at the audited participating site within 30 days of the audit. The report will include a summary of findings, participant-specific case review, recommendations on any performance and/or shortcomings and request for corrective action, when necessary. When corrective action is required, the participating site must reply within 45 days of receipt of the audit report with their corrective action plan.

